13. STATISTICAL ANALYSIS

13.1 Description of statistical methods

Parameters will be presented as mean ± SEM or median and interquartile ranges, depending on their distribution. Categorical data will be presented as counts and percentages. A two sided p-value <0.05 is considered significant. Statistical analyses will be performed with R (http://www.r-project.org). No interim analyses will be performed during the study protocol.

13.2 Analysis sets

All subjects that successfully received study medication will be included in the analyses. Subjects that completed the medical screening, but fail to attend the study day (and thus not receive study medication) will not be included in the analyses.

13.3 Participant demographics and other baseline characteristics

Demographic and other baseline characteristics (including baseline blood sample measurements) will be summarized for the placebo and Procizumab dosage groups.

13.4 Randomisation and blinding

Randomization procedures were already described in detail in section 10.2 Randomization, blinding and treatment allocation. To summarize; the randomization procedure is stratified into the three groups, consisting of eight subjects each, with sequential increased administrated doses of Procizumab. Six subjects of each group who will be treated with active medication and two subjects with placebo treatment. These groups are further divided into two randomization blocks consisting of four subjects each (1 placebo treatment and 3 active medication treatment). This is done as an extra safety measure to ensure an even spread of placebo treated subjects over all groups (so that there can never be two placebo's at the start of the trial).

A randomization list will be created by unblinded research staff prior to the treatment day. This list contains the randomization numbers, consisting of a two- digit number preceded by capital 'R' to identify this number as being the randomization number. The first digit corresponds with the randomization block (1 to 6). The second digit corresponds with the randomization number within the randomization block, starting with one (for example R.1.1 for randomization block one, subject one, followed by R.1.2, R.1.1, onwards to R.6.4). The unblinded research staff will assign a treatment group (active medication treatment or placebo treatment) at random to each number on the list. They will begin with randomization block 1 and will continue until they reach randomization block 6. A spare set of randomization numbers will be available with ascending numbers from Rep.01 onward (Rep.01, Rep.02, Rep.03 etc.) for assignment to subjects replacing subjects who were randomized but discontinued prior to administration of the study medication.

13.5 Sample size, trial power and level of significance used

As the primary endpoint is safety and no comparative statistical analyses will be performed on this endpoint, a sample size calculation is not warranted. A generally accepted group size (for dose escalating phase 1 studies) of 6 subjects per dosing group will be included (apart from the 2 placebotreated subjects per group). A sample size of 6 subjects per treatment group is regarded as being large enough to justify continuation of the trial with the next dosing group in the absence of adverse events related to the study medication. Likewise, one or more severe or serious adverse events

Radboudumc

considered to be related to the study medication could be enough to discontinue the study without a statistical difference in AE's between the groups.

13.6 Planned analysis

13.6.1 Analysis primary endpoint

Safety data will be listed by subject number and summarized descriptively by group and by dose. Only subjects that were dosed on the study day will be included in the analyses, as safety parameters cannot be assessed in subjects that did not receive study medication.

13.6.2 Analysis secondary endpoint(s)

Pharmacokinetics of Procizumab (including AUC, C_{max} , terminal $t_{1/2}$, Cl, V) will be determined for each dose and overall. Changes over time in blood plasma levels and activity of cDPP3 and other variables (vital signs, laboratory parameters, ECG, angiotensin metabolites, cytokines) within each treatment group will be described and plotted. They may be analyzed exploratory (within or between groups) by repeated measures one- or two-way analysis of variance. Data will be log-transformed if necessary.

Differences between subjects will be analyzed using Chi² tests or Fisher exact tests for counts (e.g. adverse events). T-tests, Mann-Whitney-U tests, one- or two-way analyses of variance tests or Kruskal-Wallis tests will be implemented for continuous variables, with the choice of test depending on the number of groups compared, as well as the data's distribution.

13.6.3 Analysis other study parameters/endpoints

Not applicable.

13.7 Interim analysis

Not applicable.

13.8 (Statistical) criteria for termination of the trial

There are no pre-defined statistical criteria for discontinuing parts of the clinical trial, as the coordinating investigator responsible for primary data analysis will remain blinded during the study protocol.

We also refer to section 12.10. The DSMB will perform interim analyses after completion of each study group (escalating dosages). An advice will be given whether to continue the study or make adjustments (to the protocol). The DSMB will focus on the following issues:

- Adverse events: type, severity, duration, action taken and attributability to the investigation treatment (Procizumab).
- Safety data: vital signs, laboratory safety data (hematology, clinical chemistry etc.)
- Procedures and methodology.
- Decide whether to recommend that the trial continues to recruit participants or whether recruitment should be terminated either for everyone or for some treatments groups.

13.9 Procedure for accounting for missing, unused and spurious data

Due to the small sample size spurious missing data will be imputed, if necessary, instead of deletion of the subject from the dataset. For continuous data, a missing value of a specific timepoint will be imputed by the mean of the value of the previous and next timepoint. If the last timepoint is missing,

Procizumab phase 1 study EU CT: 2023-507035-37-00 Radboudumc

the last observation is carried forward. If a subject drops out of the study prior to receiving study medication, this subject will be replaced, with a maximum of five replaced subjects. A newly recruited subject replacing a subject that dropped out will receive the treatment that was originally allocated for the subject they replace.

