A randomized, double-blind, placebo-controlled phase 1 safety study in 24 healthy male volunteers. All subjects will receive one course of treatment with study medication, being randomized to either 3 escalating doses of AK1967 (3 groups of 6, total n=18) or placebo (n=6). In each dose group, 6 volunteers will receive AK1967 and 2 placebo. Study medication will be administered as an intravenous infusion over a 2-hour period.

Trial population

24 male volunteers of 18-35 years who did not participate in other medical trials during the last 3 months. Subjects have to be healthy, defined as no clinically relevant findings during a medical screening, which includes medical history, physical examination, vital signs, 12-lead electrocardiogram and clinical laboratory parameters.

Interventions

Subjects will visit the Intensive Care department on eight occasions (screening, the treatment day of 24 hours, and on days 2 (\pm 1 hour), 3 (\pm 3 hours), 7 (\pm 1 day), 14 (\pm 2 days), 21 (\pm 3 days) and 28 (\pm 3

days)) post-treatment. After the informed consent procedure, a medical screening will be performed. This screening includes an assessment of medical history, a physical examination, checking of vital signs, a 12-lead electrocardiogram and a blood draw for laboratory evaluations.

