8.2 Definitions, derived variables and handling of missing data

Definitions of time points / time windows

Baseline will be defined per parameter and will be the value/measurement at the following timepoints:

Parameter for	Timepoint
Demographics	Screening
Vital signs	Baseline (before IMP administration)
ECG	Baseline (Screening)
Local laboratory assessment	Baseline (before IMP administration)
Arterial blood gas analysis	Baseline (before IMP administration)

Filing: https://fourteenfour.dhcvisioncloud.com/dhcvision/document.jsp?key=DATABASE:1001;IO:1527897	Page 11 of 22
---	---------------

Form Valid From: 08/03/2024

Form Version:

Record Title:

Record Title: Clinical Statistical Analysis Plan CT-P1-001

Parameter for	Timepoint
Biomarker (DPP3 concentration and	Baseline (before IMP administration)
activity)	

Derived variables

Extent of exposure:

Extent of exposure will be defined as total exposure in mg and calculated as:

total exposure
$$[mg] = 20 \frac{mg}{ml} * IMP volume [ml] * factor$$

where IMP volume is the body weight adjusted IMP volume before addition of NaCl and factor equals 1 for treatment group 12 mg/kg AK1967, 1/2 for treatment group 6 mg/kg AK1967, and 1/4 for treatment group 3 mg/kg AK1967. Total exposure will not be calculated for the Placebo treatment group.

In case of premature termination of the infusion, total exposure will additionally be multiplied by $\frac{volume\ administered\ [ml]}{c}$ in order to account for only partly administration of study drug.

Exposure per kg body weight will be calculated as:

Exposure per kg body weight
$$\left[\frac{mg}{kg}\right] = \frac{total\ exposure\ [mg]}{body\ weight\ [kg]}$$

Body mass index (BMI):

$$BMI = \frac{Weight [kg]}{Height [m]^2}$$

Handling of missing values

Data from subjects who prematurely terminate the trial will be used to the maximum possible extent. Missing values will not be inputted.

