Pharmacokinetic (PK) parameters will be calculated including area under the concentration-time curve (AUC), maximum concentration (C_{max}), time to C_{max} (Tmax), and terminal half-life (t ½).

Form Valid From: 08/03/2024

Form Version:

Record Title: Clinical Statistical Analysis Plan CT-P1-001

The maximum drug concentration (C_{max}) and time to maximum drug concentration (T_{max}) will be determined from observed values. The area under the curve (AUC_{0-t}) will be calculated for PCZ plasma concentration-time profiles using the trapezoidal method derived from non-compartmental analysis from time zero (i.e. start of drug infusion) to the last detectable concentration.

Record Title:

Data distribution will be assessed using the Kolmogorov-Smirnov test and normal/non-normal distribution will be reported. Data will be displayed both tabular and graphically as means ± SD, as well as medians ± IQR. In case a value of one of these parameters is an outlier in a subject, this will be described separately.

Dose proportionality of C_{max} and $AUC_{0-\infty}$ of the different AK1967 dose groups will be calculated by dividing the specific PK parameter by the corresponding value in the lower dose groups and comparing with the corresponding fold change in dose. This is to assess which dosage groups should be reported as being non-dose proportional.

Pharmacokinetic parameters

The following parameters will be determined from the individual plasma concentration-time profiles of AK1967 using non-compartmental methods based on actual relative sampling times:

Single concentration data will be shown with the relevant number of decimal places as provided by the analytical lab. Derived parameters, as far as they do not present single concentrations such as C_{max} , will be listed with an appropriate number of relevant digits (at least 3).

Exposure parameters (C_{max} and AUC_{0-last}) will also be dose-normalized (i.e. divided by dose) for the determination of dose-dependency.

Descriptive pharmacokinetic analyses

The PK analysis will be performed for all active treatment groups.

The individual time courses of the plasma concentrations of AK1967 will be listed and summarized descriptively by treatment group and time point.

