Summary statistics by time point will be calculated including only those samples which were taken according to the pre-defined sampling schedule, i.e.: Day 1 (0.5, 1, 1.5, 2, 3, 4, 5, 6, 7, 8, 9, 10, 24 hour ± 2 mins), Day 2 (± 1 hour), Day 3 (± 3 hours), Day 7 (± 1 day), Day 14 (± 2 days), Day 21 ((± 3 days), and Day 28 (± 3 days).

For the calculation of summary statistics, when data is reported as BLQ and ALQ (below and above limit of quantification, respectively), the low and high limit of detection value will be used in the analysis to obtain the means, standard of deviations, coefficient of variation, medians and interquartile ranges.

Form Valid From: 08/03/2024

Form Version:

Record Title:

Record Title: Clinical Statistical Analysis Plan CT-P1-001

Individual plasma concentration-time profiles will be plotted for AK1967 (up to 6 profiles in one plot) for each dose group considering all subjects with available PK concentration data using actual relative sampling times. Mean (SD), as well as median (IQR) of AK1967 plasma concentrations will be plotted for all active treatment groups. Individual and geometric mean concentration versus time curves will be plotted using both linear and semi-logarithmic scaling.

Summary statistics will be calculated for each pharmacokinetic parameter by dose group based on PKs.

Pharmacodynamic data analyses (effects of AK1967 on DPP3 enzyme activity, concentration, reninangiotensin and adrenergic system metabolites)

- To determine the effects of AK1967 on DPP3 activity and concentration in healthy male volunteers.
- To determine the effects of AK1967 on renin-angiotensin system metabolites in healthy male volunteers.
- To determine the effects of AK1967 on circulating adrenergic metabolite concentrations in healthy male volunteers.
- To determine the effects of AK1967 on inflammatory cytokines, including, but not limited to TNF, IL-6, IL-8, IL-10.

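### Protocol 13.9 allows neighbour-mean and LOCF imputation, SAP 8.2 rules imputation out, and the protocol rule does not suit the widely spaced late drug concentrations

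*Protocol*

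**What the plan says.** Protocol 13.9 opens with a condition: "Due to the small sample size spurious missing data will be imputed, if necessary", as an alternative to removing the subject. For continuous data, "a missing value of a specific timepoint will be imputed by the mean of the value of the previous and next timepoint". When the final timepoint is the missing one, "the last observation is carried forward". No class of continuous variable is exempted, so the text covers drug concentrations.

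SAP 8.2, under its paragraph on missing values, says "Missing values will not be inputted". From its place in the text, the verb must mean imputed.

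Nothing settles the difference. SAP 7.2 mentions missing data in its title but only points to a data review plan. Protocol 13.10 only provides that deviations are recorded in a note to file.

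SAP 8.6 gives the PK sampling schedule: "Day 1 (0.5, 1, 1.5, 2, 3, 4, 5, 6, 7, 8, 9, 10, 24 hour ± 2 mins"), then days 2 and 3, then "Day 7 (± 1 day), Day 14 (± 2 days), Day 21 ((± 3 days), and Day 28 (± 3 days"). AUC "will be calculated for PCZ plasma concentration-time profiles using the trapezoidal method", without saying linear or logarithmic. Terminal half-life and volume are named secondary endpoints (Protocol 13.6.2, SAP 5.2). Protocol 3.1(f) says only that the half-life is short for an IgG1.

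**The concern.** Two analysts who each follow one of the documents would produce different datasets from the same trial. The protocol's condition does not resolve this, because it does not say when imputation becomes necessary. The choice could therefore be made after the data are seen.

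The protocol rule also assumes that a variable runs roughly straight, or stays flat, between visits. A drug concentration after the end of infusion does neither. From day 3 onward the gaps are 4 to 7 days, which may span several half-lives. An imputed late value can then be far too high, and it enters the group summary as if it had been measured. With 6 subjects per active dose group, one such value is visible in the mean. The terminal slope is the PK quantity most exposed, because it is estimated from those same late samples.

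**Working it through.** The plan states no figure for missing data, so there is none to reproduce.

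**Inputs.** The sampling times are those in SAP 8.6; Protocol 10.3 places the two visits after 24 h at 48 h and 72 h. The infusion lasts 2 h (Protocol synopsis). There are 6 subjects per active group (Protocol 13.5). The half-life h is assumed, with 2, 5 and 10 days shown. Decline is assumed mono-exponential, C(t) = C0 × 2^(−t/h).

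**Single late concentrations.** With equal gaps of d days, the neighbour mean divided by the true value is [2^(d/h) + 2^(−d/h)]/2. LOCF divided by the true value is 2^(d/h). Day 7 has unequal gaps, so its ratio is [C(3) + C(14)]/[2 × C(7)].

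| Missing sample | h = 2 d | h = 5 d | h = 10 d |
|---|---|---|---|
| Day 7, neighbour mean | 2.04 | 1.06 | 0.97 |
| Day 14, neighbour mean | 5.70 | 1.51 | 1.12 |
| Day 28, LOCF from day 21 | 11.3 | 2.64 | 1.62 |

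For example, day 14 at h = 2 is (2^3.5 + 2^−3.5)/2 = (11.31 + 0.09)/2 = 5.70.

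**Group summary.** If six subjects share the same true day-14 value and one is imputed at 5.70 times it, the arithmetic mean rises by (5 + 5.70)/6 − 1 = 78%. The geometric mean rises by 5.70^(1/6) − 1 = 34%.

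**Terminal half-life.** Let y be log concentration at days 14, 21 and 28. The least-squares slope through three equally spaced points is (y28 − y14)/14. LOCF sets y28 = y21, so the slope becomes (y21 − y14)/14. On a straight log-linear decline this is half the true slope, so the half-life doubles for any h (48 h becomes 96 h, for instance). Volume is clearance divided by the slope, so at a given clearance it doubles too. The neighbour mean does less harm here: with day 14 imputed and a fit to the last four visits, 48 h becomes 44.8 h.

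**Where the rule works.** At 4 h and 7 h the ratio is 1.00, and the same holds across the hourly samples from 3 to 9 h. The end-of-infusion sample at 2 h comes out at about 0.87 of the true value, because its neighbours lie on either side of the peak.

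**AUC to the last sample, linear trapezoid.** At equal spacing the neighbour mean lies on the straight line between its neighbours, so imputing and omitting give the same area. For day 14 at h = 2 both are 8.3% above the area from the complete profile. For day 7 at h = 2, imputing gives +16.4% and omitting +24.8%. LOCF at day 28 changes this area by 0.07% at h = 2, 1.6% at h = 5 and 2.5% at h = 10. A log-linear trapezoid follows an exponential decline exactly, so omission then costs nothing under the same assumption.

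**The case against.** The strongest reply is that the protocol rule is conditional and meant for isolated gaps, that the SAP, as the detailed analysis document, already holds the better rule, and that most PK samples are dense. Much of this stands. Only four of the 19 post-dose PK samples follow a gap of 4 to 7 days. The size of the error depends on a half-life that the documents do not give. At very short half-lives, late values may fall below quantification, where SAP 8.6 substitutes a limit value, so the largest ratios might not arise. What the reply does not supply is a statement of which document prevails, or an exemption for concentrations.

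A reader might infer more than the documents support:

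- **That imputation corrupts AUC and clearance.** For a single missing visit at day 7 or 14, the linear-trapezoid area to the last sample is no worse imputed than omitted. At a 2-day half-life only 2^−7, about 0.8%, of the total area lies beyond day 14. SAP 8.6 also uses an area extrapolated to infinity without giving the extrapolation rule; the point does not rest on that either.
- **That the rule is wrong for drug concentrations in general.** It is accurate from 3 to 9 h, and at a 10-day half-life it is only 12% high at day 14.
- **That safety results are distorted.** The documents give no time course from which to calculate this for laboratory values or DPP3 activity, and safety data are also listed subject by subject.

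**Conclusion.** The contradiction is certain and needs no assumption: one document permits imputation, the other excludes it, and neither gives precedence.

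The unsuitability of the protocol rule holds for the late PK visits. The size rests on mono-exponential decline and an assumed half-life: 1.12 to 5.7 times the true value for a neighbour mean at day 14, and 1.6 to 11.3 times for LOCF at day 28, over half-lives of 10 down to 2 days. The doubling of terminal half-life under LOCF at day 28 does not depend on the true half-life. It does require a log-linear fit to the last three visits, which the SAP does not specify, and a quantifiable day-21 sample. Any volume derived from that slope is biased with it.

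This should be corrected before analysis. It does not threaten the descriptive review of the primary safety endpoint.

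**What to change.** Delete the neighbour-mean and LOCF rules from Protocol 13.9 and state the SAP's no-imputation rule in both documents, correcting the verb in SAP 8.2. State that PK parameters, terminal half-life in particular, are calculated from observed concentrations only. Add to SAP 8.6 that the trapezoid is log-linear in the declining phase. Without this, omitting a late sample under a linear trapezoid still inflates AUC.

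The cost is one protocol paragraph, one SAP sentence on the trapezoid, and tables in which n varies by time point.

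Optional and separate: the repeated-measures ANOVA planned in SAP 8.6 and 8.7, in its classical form, drops any subject with a gap, which is the loss that Protocol 13.9 sets out to avoid. A likelihood-based mixed model would keep all observed values. It needs edits to both SAP sections and is not required to settle the contradiction.

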13.10 Procedure for reporting any deviation(s) from the original statistical plan

In case deviations from the original statistical plan are necessary, this will be documented in a note to file.

14. ETHICAL CONSIDERATIONS

14.1 Declaration of Helsinki

The sponsor will ensure that this study is conducted in accordance with the ethical principles that have their origins in the declaration of Helsinki.

14.2 Recruitment and informed consent procedures

Informed consent will be obtained prior to any study related procedures being undertaken at screening. Informed consent will be written, dated and signed by the investigator performing the interview, and by the subject. The investigator or his/her representative will explain the nature of the study to the subject and answer all questions regarding this study. In the interview it will be verified that the subject has understood the information. The subject will be provided with a copy of the document (or the record) by which informed consent has been given. The informed consent will be documented. Adequate time will be given for the subject to consider his decision to participate in the clinical trial, with a minimum decision time of 48 hours.

Healthy subjects will be recruited by posters at several faculties on the campus of the Radboud University Nijmegen and online. Interested people will be emailed the subject information document. Subjects will be given at least one day to consider their decision. On screening day, subjects will be informed about the study by the coordinating investigator (research-physician) and their remaining questions will be answered. Finally, they can sign and date the informed consent in the presence of the investigator. Two identical informed consent forms will be signed and dated, one for the subject and one for the investigator.

